6.4. After Hours Visits

Pregnant women will be encouraged to come to the TDH maternity ward (open 24 hours a day) and parents/guardians will be encouraged to bring their child to the TDH pediatric inpatient ward (open 24 hours a day) when urgent care is needed outside of study clinic hours. Pregnant

women or parents/guardians of children will be instructed to inform hospital personnel of their involvement in the study at the time of registration and to visit the study clinic on the following day. If a patient is diagnosed with uncomplicated malaria they will receive treatment from a hospital supply of AL and the doctors will be instructed to refer patients to our study clinic when it opens at 8 am the following day. If a patient is diagnosed with severe malaria, he/she will receive quinine or artesunate following standard treatment guidelines. Patients with non-malarial illnesses will be managed at the discretion of the Tororo District Hospital staff. Upon discharge, patients will receive follow-up at the study clinic as outlined above. Study personnel will visit the Tororo District Hospital daily to inquire about visits from study subjects and facilitate follow-up in the study clinic.

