6.2. Diagnosis and Management of Malaria

Patients found to have malaria based on laboratory confirmation will have a second finger prick for a thin smear (to determine parasite species), hemoglobin measurement using a portable spectrophotometer (HemoCue), and collection of plasma for future PK studies. All episodes of malaria will be classified as uncomplicated or complicated based on the following criteria:

Uncomplicated malaria (all of the following)

- 1) Fever ($\geq 38.0^{\circ}\text{C}$ tympanic) or history of fever in the previous 24 hours
- 2) Positive thick blood smear
- 3) Absence of complicated malaria

Complicated malaria (any of the following)

- 1) Evidence of severe malaria (Appendix F) and parasitemia
- 2) Danger signs present in children (Appendix F) and parasitemia

Episodes of malaria will also be classified into the following categories according to the timing of previous malaria episodes for treatment purposes:

1. New episodes of malaria will be defined as any first episode or any episode occurring > 14 days after the diagnosis of a previous episode
2. Treatment failures will be defined as any of the following:
 - a. Complicated malaria occurring 1-14 days after the diagnosis of a previous episode
 - b. Fever ($\geq 38.0^{\circ}\text{C}$ tympanic) or history of fever in the previous 24 hours with a parasite density \geq the parasite density of an episode of malaria diagnosed 2 days prior

- c. Fever ($\geq 38.0^{\circ}\text{C}$ tympanic) or history of fever in the previous 24 hours with a parasite density $\geq 25\%$ of the parasite density of an episode of malaria diagnosed 3 days prior
- d. Fever ($\geq 38.0^{\circ}\text{C}$ tympanic) or history of fever in the previous 24 hours with a positive thick blood smear of any parasite density occurring 4-14 days after the diagnosis of a previous episode

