All patients diagnosed with new episodes of uncomplicated malaria will be prescribed AL, the recommended first-line treatment in Uganda for children and pregnant women in their 2nd or 3rd trimester. Patients with complicated malaria will be prescribed quinine or artesunate according to national malaria treatment guidelines. Children who are less than 4 months of age or weigh $<5\text{kg}$, will be treated with quinine for uncomplicated malaria in accordance with the Uganda Ministry of Health Guidelines. Patients with treatment failure within 14 days following treatment with AL will be prescribed quinine according to national malaria treatment guidelines. Patients with treatment failure within 14 days following treatment with quinine or artesunate will be treated with quinine plus clindamycin or artesunate.

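### Section 6.4 gives AL to every after-hours patient with uncomplicated malaria, where section 6.2 assigns other drugs to young infants and to treatment failures (minor inconsistency)

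*Protocol*

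**What the plan says.** Protocol section 6.2 (Diagnosis and Management of Malaria) contains five drug rules:

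- The general rule: "All patients diagnosed with new episodes of uncomplicated malaria will be prescribed AL".
- For complicated malaria: "Patients with complicated malaria will be prescribed quinine or artesunate according to national malaria treatment guidelines".
- For children under 4 months of age or under 5 kg, who "will be treated with quinine for uncomplicated malaria in accordance with the Uganda Ministry of Health Guidelines".
- For failure after AL: "Patients with treatment failure within 14 days following treatment with AL will be prescribed quinine according to national malaria treatment guidelines".
- For failure after the other drugs: "Patients with treatment failure within 14 days following treatment with quinine or artesunate will be treated with quinine plus clindamycin or artesunate".

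Protocol section 6.4 (After Hours Visits) covers patients seen on the hospital wards while the study clinic is closed. For uncomplicated malaria it says: "If a patient is diagnosed with uncomplicated malaria they will receive treatment from a hospital supply of AL". For severe malaria it gives quinine or artesunate under standard guidelines. It also has ward doctors refer patients to the study clinic at 8 am the next day, and has study staff visit the hospital every day to ask about participants.

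**The concern.** The two sections name different drugs for the same diagnosis in some patients. Section 6.4 applies at the hours when care is given by ward staff rather than by the study clinic, so it is the section those staff would most naturally be shown. Followed as written, it gives AL to an infant for whom 6.2 requires quinine. It also repeats AL in a patient whose AL course has just failed, and gives AL after failed quinine or artesunate, where 6.2 names a different regimen.

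What is at stake is the correct choice of rescue drug for a few vulnerable patients. The trial's estimates are not at stake.

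**Working it through.** No arithmetic of the trial's own is involved, so the check sets the two sections side by side.

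| Situation | Section 6.2 | Section 6.4 |
|---|---|---|
| New uncomplicated episode, none of the situations below | AL | AL |
| Complicated malaria | Quinine or artesunate | Quinine or artesunate, but for severe malaria |
| Uncomplicated, under 4 months or under 5 kg | Quinine | AL |
| Uncomplicated failure within 14 days of AL | Quinine | AL |
| Uncomplicated failure within 14 days of quinine or artesunate | Quinine plus clindamycin, or artesunate | AL |

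Section 6.4 carries over two of the five rules and omits 5 − 2 = 3. For those three it is not merely silent: its general sentence supplies a different drug.

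**Are these patients in the trial?** Section 3 follows children from birth, so every enrolled child who remains in follow-up passes through the age range of the infant rule.

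**Can a treatment failure be uncomplicated, and so fall under the AL sentence of 6.4?** Section 6.2 lists four failure criteria. Only the first requires complicated disease: "Complicated malaria occurring 1-14 days after the diagnosis of a previous episode". The other three (4 − 1 = 3) rest on fever, or a history of fever, with a positive smear. The last needs only fever "with a positive thick blood smear of any parasite density occurring 4-14 days after the diagnosis of a previous episode". So an uncomplicated failure is possible.

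**Does other wording in 6.4 settle the matter?** The reference to standard guidelines is attached to severe malaria only. The reference back to what was outlined above concerns follow-up after discharge, not the choice of drug. Neither brings in the exceptions of 6.2.

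**Is an outcome touched?** Sections 8.2.1 and 8.3.1 count malaria treatments not preceded by another treatment in the previous 14 days. The definition does not depend on which drug was given, and the figures in section 8.4 do not use it either.

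**The case against.** The strongest reply is that the sections can be reconciled. Section 6.2 is the malaria management section, and its rules are not limited by hour or place. Section 6.4 reads as logistics (which ward, whose drug supply, when to refer) and does not say that it replaces 6.2. A careful reader could apply the specific infant and failure rules on top of the general AL sentence. This is a fair account of what was probably intended, and it is why the point is minor. It does not remove the conflict, because 6.4 states a drug rule for any patient and is addressed to care given by hospital staff outside the study clinic.

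A related reply is that 6.2 must already apply after hours, since 6.4 names no drug for a child with danger signs short of severe malaria. That case differs. There 6.4 is silent and 6.2 can fill the gap; for young infants and failures, 6.4 names a drug that 6.2 does not.

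The safeguards also stand. Section 6.2 attributes the infant rule and the failure-after-AL rule to Ministry of Health or national guidelines, which the wards may follow anyway. Participants are told to disclose their enrolment, patients are referred the next morning, and study staff visit daily. Only the rule for failure after quinine or artesunate has no guideline attribution.

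Two stronger readings should be resisted:

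- A reader might infer that the missing reference to 6.2 shows a deliberate separate rule, since sections 4.4 and 6.5 do cite 6.2 for treatment. The protocol is not consistent enough for that. Section 6.1 goes from a positive smear to a malaria diagnosis without citing 6.2, and section 6.3 refers only to management per the study protocol.
- A reader might take the clinic's closing hours, 5 p.m. to 8 a.m., as a 15-hour limit on exposure. They are not a limit, because attendance the next day is instructed and not assured.

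**Conclusion.** The inconsistency is real and minor. For three situations in 6.2, section 6.4 taken literally gives AL where 6.2 gives another regimen, until the study clinic reviews the patient. This rests on reading the AL sentence of 6.4 as it stands, without importing exceptions that it does not mention.

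The practical reach is small, given the guideline attribution of two of the three rules, the next-morning referral and the daily hospital visits. The number of affected episodes cannot be derived, because the protocol gives no after-hours visit rate, no malaria rate under 4 months and no failure rate after AL or quinine in this setting. The counts of rules and criteria above describe the text and do not measure risk.

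A reader might also infer that malaria incidence would be distorted. The documents do not support this: the outcome counts treatments whatever the drug, and the sample size figures are untouched.

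**What to change.** Amend section 6.4 to say that after-hours malaria is treated according to section 6.2: AL for new episodes of uncomplicated malaria, except in children under 4 months or under 5 kg and in treatment failures within 14 days, who are treated as in 6.2. In the next rule of 6.4, change severe malaria to complicated malaria, so that children with danger signs are visibly covered and the terms match 6.2. Pass the amended text to the maternity and pediatric wards.

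The cost is one sentence, one word and a notice to two wards. No patients, visits, procedures or participant documents are added. Section 6.4 already has the hospital giving quinine or artesunate for severe malaria, so the main alternative drugs are not new to after-hours care.

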6.5. Routine Assessments

Routine assessments will be done in the clinic every 4 weeks for both pregnant women and children. Study participants not seen in the clinic for their every 4 week routine visits will be visited at home and requested to come to the study clinic as soon as possible. Pregnant women and children will receive standards of care as designated in the Uganda MOH guidelines (Appendix G). Routine antenatal care will include screening and treatment for sexually transmitted Infections, blood pressure assessment, urine dipstick for proteinuria, prescription of iron, folate, multivitamins and mebendazole. Routine care in children will include immunizations, vitamin A supplementation, and management of anemia using Integrated Management of Childhood Illness (IMCI) guidelines. During routine assessments subjects will be asked about visits to outside health facilities and the use of any medications outside the study protocol. The study protocol will be reinforced with discussion regarding the need to come to the study clinic promptly upon the onset of any illness and to avoid use of outside medications. Standardized assessment of adherence will also be done for study drugs administered at home and ITN use. A routine history and physical exam will be performed using a standardized clinical assessment form. Blood will be collected by finger prick (in very young children, heel sticks may be substituted for finger pricks) for thick smear, collection of plasma for PK studies, and filter paper samples. If a pregnant woman or parent/guardian of a child reports a fever in the last 24 hours or the patient has a documented temperature $\geq 38.0^{\circ}\text{C}$ tympanic, the patient's thick blood smear will be read immediately and if positive the patient will be diagnosed and treated for malaria (see section 6.2). Phlebotomy for routine laboratory tests (CBC and ALT) to monitor for potential adverse events from study medications and for immunology studies will be performed every 8 weeks in pregnant women and every 16 weeks in children. Screening for non-malaria parasitic infections will be performed once in pregnant women after the 1st trimester at the time routine mebendazole is administered and in children at 1 year of age.

Screening will consist of stool ova and parasite examination, circulating filarial antigens (by ICT card for *Wucheria*), and blood smear for microfilaremia (including *Mansonella perstans*) using Knott's technique. For pregnant women and children 2-24 months of age, study drugs will be administered at the time of each routine visit as described in sections 5.3 and 5.4.

6.6. Delivery visit

Addressing one of the main study outcomes, placenta malaria, requires collection and processing of specimens at delivery. Systems will be in place to facilitate a birth plan which will encourage women to come to the hospital for delivery, including access to transportation 24 hours a day. However for women who are unable to travel to the hospital for delivery or choose to deliver at home, a study staff member will be driven to the home to follow study procedures. Study staff will document details of the delivery, including date and time, type of delivery, estimated blood loss and any maternal, obstetrical or neonatal complications. Study staff will document the infant's Apgar score and birth weight with calibrated scales. Biological samples collected at the time of delivery will include maternal venous blood (for thick blood smear, filter paper samples, CBC, ALT, immunology studies, and PK studies), cord blood (for thick blood smear, filter paper samples, hemoglobin measurement, and immunology studies) and placental tissue. Following delivery, neonatal care, as per national guidelines, will include polio and BCG immunization, ophthalmic tetracycline, vitamin K, and vitamin A supplementation.

At the time of delivery, women will undergo repeat rapid HIV testing based on national guidelines. If women are found to have become HIV-infected during pregnancy, both the mother and their newborn will be withdrawn from the study and immediately referred for care following local prevention of mother-to-child transmission (PMTCT) guidelines.

6.7. Postpartum visits.

Women will be evaluated within 1 week following delivery and 6 weeks postpartum as part of routine care. Both visits will include an abdominal exam syndromic management of STIs, and follow-up on any obstetrical complications that occurred including evaluation of the neonate for any congenital abnormalities. Pelvic and breast exam will be done if clinically indicated. Contraceptive counseling, nutritional assessment and infant feeding and support will be provided. Following the 6 weeks visit, women will no longer be considered study participants, although most will remain primary care givers for their children enrolled in the second phase of the study.

Summaries of all procedures done during routine visits in pregnant women and children are presented in Appendix H and I, respectively.

6.8. Medical Care Outside the Study Clinic

We will provide routine medical care in our clinic free of charge, including medications, to the extent possible given resources available. Study participants and their guardians will be reimbursed for costs of any transportation to and from our clinic. In addition, we will reimburse the cost of tests and drugs for referrals of study participants made by study physicians to other clinics and services as well as after-hours visits at TDH. We anticipate reimbursing the cost of most diagnostic tests (including laboratory tests, X-rays, and ultrasounds) and medications resulting from these referrals, using available funds. However, reimbursement of all diagnostic tests and treatment recommended outside the study clinic cannot be guaranteed in all circumstances. Decisions on reimbursement will be made by the study coordinator and the investigators, in conjunction with the funding agency if necessary.

6.9. Duration of Follow-up and Criteria for Premature Study Withdrawal

Pregnant women will be followed until their 6 week postpartum visit. Children will be followed through 30th June 2018 until they reach 36 months of age. Women will be asked to bring in the biological father to the study clinic for informed consent discussion when child is born. He will be asked to provide written consent or a fingerprint to allow participation of the infant. If a father is unknown or unavailable, the woman will document in accordance with UNCST guidance and participation will continue for both the woman and infant. If the biological father refuses consent for the child's participation, the child will not be enrolled.

Study participants will be prematurely withdrawn from the study for: 1) movement out of study area or inability to be located for > 60 consecutive days, 2) withdrawal of informed consent, 3) inability to comply with the study schedule and procedures, 4) at the discretion of the site investigator if the study is not in the best interest of the participant, 5) subject or parent/guardian judged by the site investigator to be at significant risk of failing to comply with the study protocol as to cause them harm or seriously interfere with the validity of study results, 6) women found to have become HIV infected at the time of delivery, or 7) father does not consent to the child's participation (child withdrawal only). If a subject is withdrawn for reasons # 1 or 2, we will be unable to perform any additional study procedures. If a subject is withdrawn for reasons # 3-5, plans to obtain appropriate follow-up tests outside of the study will be individualized for each subject depending on the health status of the subject at the time of withdrawal and the willingness of the participant and his or her parent/guardian to proceed with additional testing. If a subject is withdrawn for #6-7, the will be referred for appropriate care following local PMTCT guidelines.

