6.14. Grade 3 or 4 Adverse Events

Management will be as follows:

- Repeat observation or lab test within 72 hours of observation or of receiving lab results report.
- For grade 3 or non-life threatening grade 4 adverse events, subjects may continue taking study drugs pending clinic visit or repeat laboratory tests. Clinician has the option of immediately stopping the study drugs if subject cannot be examined in clinic, if a repeat laboratory test cannot be performed within 72 hours, or if the clinician determines that the continuation of study drugs is unsafe while awaiting clinic exam or test results.
- For grade 4 life-threatening adverse events, study clinicians should hold study drugs pending laboratory confirmation.
- Work-up to exclude other causes.
- For all grade 3 or 4 adverse events supported by repeat clinical exam or laboratory test results, study drugs will be held, and laboratory tests will be repeated every 1-2 weeks, until the adverse event resolves to \leq grade 2 unless there is strong evidence that the adverse event is not related to either study drug.
- If the adverse event persists at grade 3 or 4 for more than 28 days or recurs on re-challenge, and the adverse event is thought to be possibly related to one of the study drugs, the study drugs will be permanently discontinued.

In the event that study drugs are permanently discontinued, study participants will remain in the study, following our intention-to-treat analysis approach. In the event that study drugs are permanently discontinued, study clinicians may become un-blinded to the study participant assigned treatment regimen if this knowledge may assist in the management of the grade 3 or 4 adverse event(s) that lead to the permanent discontinuation of the study drugs.

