8.1.3. Analyses

An intention-to-treat approach to all analyses will be used, including all study participants randomized to therapy and including all follow-up time until the study participants complete the study or early study termination regardless of whether the intervention was stopped due to an adverse event.

Primary analysis. We will compare the prevalence of placental malaria defined by histopathology at birth between the study arms using the Chi-Square test for all pair-wise comparisons. We will explore for any differences of potential confounders between the treatment arms and if necessary adjust our analysis using multivariate logistic regression.

Secondary analyses. We will compare the prevalence of placental parasitemia and our composite birth outcome using the Chi-Square test. We will compare the incidence of maternal malaria and adverse events using Poisson or negative binomial regression models. The Poisson models will include the logarithm of the follow-up time as an offset. We will translate the fitted coefficients and their confidence bounds into percentage effects with the formula $100 * [\exp(\text{coefficient}) - 1]$. This approach is closely related to exponential survival models for analyzing events per follow-up time, but is better able to adjust for violated assumptions. Testing for overdispersion in the Poisson regression can detect violations of these assumptions, and variances can be adjusted accordingly to produce valid p-values and confidence interval. If significant deviations from required distributions in study data are detected, we will employ negative-binomial or zero-inflated negative-binomial models to account for the observed pattern of data. We will compare the prevalence of maternal anemia and asymptomatic parasitemia using generalized estimating equations with adjustments for repeated measures in the same study participant. If necessary, multivariate analyses will be performed to adjust for potential confounders and effect modifiers.

8.2. Hypothesis 2

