8.2.3. Analyses

An intention-to-treat approach to all analyses will be used, including all infants born to mothers assigned to receive IPTp with 3 dose DP or monthly DP and including all follow-up time until the

study participants reach 24 months of age or early study termination regardless of whether the intervention was stopped due to an adverse event.

Primary analysis. We will compare the incidence of malaria using Poisson or negative binomial regression models as described in section 9.1.3. In necessary, multivariate analyses will be performed to adjust for potential confounders and effect modifiers.

Secondary analyses. We will compare the incidence of complicated malaria, hospitalizations, and adverse events using Poisson or negative binomial regression models as described in section 9.1.3. We will compare the prevalence of anemia, asymptomatic parasitemia, and gametocytemia using generalized estimating equations with adjustments for repeated measures in the same study participant. In necessary, multivariate analyses will be performed to adjust for potential confounders and effect modifiers.

8.3. Hypothesis 3

We will test the hypotheses that A) infants born to mothers randomized to receive IPTp with 3 dose DP or monthly DP will have a lower incidence of malaria during the first 24 months of life compared to infants born to mothers who were randomized to receive IPTp with 3 doses of SP, and, B) infants randomized to receive monthly DP between 2-24 months of age will have a lower incidence of malaria between 24-36 months of age after the intervention is stopped compared to infants randomized q 3 monthly DP between 2-24 months of age. For hypothesis 3A, we will only include infants randomized to receive q 3 monthly DP during infancy. For hypothesis 3B, we will also explore for interaction with the intervention given during pregnancy.

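### Section 6.9 ends study participation for non-compliance, actual or predicted, with no commitment to collect outcomes afterwards, and this is not reconciled with the intention-to-treat plan in 8.1.3 or the rule in 6.14.

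*Protocol*

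**What the plan says.** Protocol section 6.9 lists seven grounds for premature withdrawal from the study. Reason 3 is "inability to comply with the study schedule and procedures". Reason 5 covers a participant "judged by the site investigator to be at significant risk of failing to comply with the study protocol", qualified by a threshold of harm to the participant or serious interference with the validity of the results. For reasons 3 to 5, "plans to obtain appropriate follow-up tests outside of the study will be individualized for each subject". No trial outcome is promised.

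Reason 6 is HIV infection in the mother found at delivery. Section 6.6 adds that "both the mother and their newborn will be withdrawn from the study", with referral for care.

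The analysis sections are worded differently:

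- Section 8.1.3 (Hypothesis 1) declares intention-to-treat, "including all study participants randomized to therapy and including all follow-up time until the study participants complete the study or early study termination".
- Section 8.2.3 (Hypothesis 2) declares the same, "including all infants born to mothers assigned to receive IPTp with 3 dose DP or monthly DP".
- Section 6.14 covers permanent discontinuation of study drug after an adverse event: "study participants will remain in the study, following our intention-to-treat analysis approach".

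**The concern.** All of these withdrawals come after randomisation, which takes place at enrolment, and they are imposed by the trial. Reasons 3 and 5 select on compliance. Section 6.5 gives study drug at the routine visits, so a participant who cannot keep the schedule is also likely to miss doses, and missed doses can change malaria risk. If such people leave and their outcomes are not sought, the comparison moves away from the randomised groups and towards those who complied.

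Section 6.14 uses intention-to-treat as its reason for keeping people in the study after drug is stopped. Section 6.9 gives no reason for treating non-compliance differently. What is at stake is the completeness of the primary placental outcome and, for infants, whether follow-up ends for reasons unrelated to malaria risk.

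**Working it through.** **1. The plan's own figures.** Section 8.4 assumes that 90% of women reach the endpoint and that 5% of infant follow-up time is lost per year.

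- Women: 100 × 0.90 = 90 per arm (Table 9: 90).
- Infants: 90 × 0.95² = 81.2 (Table 9: 81); 45 × 0.95² = 40.6 (Table 9: 41).
- Table 10 gives a detectable reduction of 33% from a control prevalence of 62%, so the DP prevalence is 0.62 × 0.67 = 0.4154. With 90 per arm, a pooled two-proportion test and two-sided alpha 0.05: z = (0.2046 × √90 − 1.96 × 0.7067) / 0.6917 = 0.804, power 78.9%. The detectable difference at 80% power is 33.5%.

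The figures reproduce. Loss of numbers is already allowed for, and no stated figure is wrong. An allowance for numbers does not, however, deal with selective loss.

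**2. Effect on Hypothesis 1.** The primary outcome (8.1.1) is a yes/no histology result from tissue taken at delivery (6.6, 6.10.3), compared by chi-square (8.1.3). It has no partial contribution: a woman withdrawn before delivery has no result.

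**3. Effect on infant incidence.** Sections 8.2.1 and 8.3.1 end time at risk at early termination. A withdrawn child stays in the assigned arm, and episodes and time before withdrawal count. The issue is censoring. A newborn withdrawn at birth under 6.6 contributes almost no time at risk, although 8.2.3 includes all infants born to mothers in the DP arms.

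**4. Illustration of size, Hypothesis 1.** The protocol gives no expected withdrawals by reason, so the following are assumptions: a fraction f of a DP arm is withdrawn before delivery, these women carry the SP-arm risk of 62%, and the observed SP risk stays at 62%. The observed DP risk is then (0.4154 − 0.62f)/(1 − f).

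| f | Observed DP risk | Apparent reduction (true 33%) |
|---|---|---|
| 0.05 | 0.3844/0.95 = 0.4046 | 34.7% |
| 0.10 | 0.3534/0.90 = 0.3927 | 36.7% |

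The same model read the other way: if 33% is the reduction among those kept, the reduction among all randomised is 0.33 × (1 − f), or 31.4% and 29.7%.

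**5. Outer bounds.** Take 33% observed in 90 women per arm (55.8 and 37.4 events) and set the 10 missing women per arm, whatever the reason, to the extremes.

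- All missing DP women positive, all missing SP women negative: 1 − 0.474/0.558 = 15%.
- The reverse: 1 − 0.374/0.658 = 43%.

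The bounds lie on both sides of 33%, so the documents do not fix the direction.

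**The case against.** The strongest reply has five parts.

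- **The intention-to-treat text itself stops at early termination.** A reader might infer that 6.9 contradicts intention-to-treat or removes people from the analysis set. No passage does so; incidence outcomes are censored in the assigned arm. This stands for the infant outcomes. It does not help the placental outcome, which either exists or does not. A statistical analysis plan could say how missing results are handled, but it cannot recover outcomes that the protocol does not commit to collect.
- **Reasons 3 and 5 are not plain drug-adherence rules.** Reason 3 names schedule and procedures, and reason 5 contains a harm clause. Both remarks are right, and the harm clause should stay. Reason 5 is nevertheless a prediction, so it can apply to someone who still attends and whose outcome could be obtained.
- **Blinding and matching placebos give every arm the same visits.** This makes differential use of the criteria less likely. It does not make risk equal between those who leave and those who stay.
- **The earlier Tororo trial is a poor guide.** Section 1.2 suggests that most DP children were not compliant when diagnosed with malaria. A reader might infer that withdrawals would remove malaria episodes selectively from the DP arms, or might scale up that trial's 58% efficacy. But dosing there was open-label and unsupervised, the comparator was no chemoprevention (not the comparison in Hypothesis 2), and episodes before withdrawal count here.
- **The assumed 5-10% is high for these reasons alone.** The plan allows 10% of women without the endpoint for all causes. This stands; the range is an illustration, not a forecast.

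**Conclusion.** The point holds as a lack of reconciliation between sections 6.9 and 6.6 on one side and 6.14, 8.1.3 and 8.2.3 on the other. Women withdrawn before delivery drop out of the primary Hypothesis 1 analysis. For infants, withdrawal linked to compliance may be informative censoring.

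The size is unknown. The illustration moves a true 33% reduction to about 35-37%. That shift is small beside the sampling error: with 90 women per arm, the standard error of the log risk ratio is √(0.38/55.8 + 0.5846/37.4) = 0.150, so the 95% interval around a 33% reduction runs from about 10% to 50%.

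Two further inferences are not supported. One is that the bias must favour the more intensive regimen. If those withdrawn have the same risk as the rest of their arm there is no bias, and the bounds above allow either sign. The other is that placentas of women found HIV-infected at delivery are thrown away. Tissue is taken around the same visit as the HIV test, and the text is silent on its use.

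This is a worthwhile, low-cost improvement to a stated rule, not a fatal flaw.

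**What to change.** Amend section 6.9 so that withdrawal under reasons 3 and 5 does not by itself end outcome collection. Where consent is not withdrawn and the participant can be reached, continue to record delivery and placental outcomes and malaria episodes, and analyse them in the assigned arm.

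For reason 6, state in 6.6 and 6.9 that delivery and placental data already collected from the mother are kept in the Hypothesis 1 analysis.

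The harm clause in reason 5, referral for care and all decisions on study drug stay as they are.

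The cost is mainly protocol wording, since the clinic, home visits and delivery attendance already exist. The downside is some continued visits for participants who attend poorly.
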